**Table 1-2: Schedule of Activities**

Study Period	Screening Period a	Main Treatment Period						Extension Treatment Period	EW/ Withdrawal Visit b,w	SFU Visit (In-clinic) c	Rescue Therapy Visit (If applicable) d
		Baseline e (In-clinic)	Week 1 (Phone call)	Week 2 (In-clinic)	Week 4 (Phone call)	Week 8 (Phone call)	Week 12 (In-clinic)				
Visit name	Screening Visit (In-clinic)							Week 24, 36, 48... every 12 weeks (In-clinic)			
Visit #	1	2	3	4	5	6	7	8, 9, 10...	–	–	–
Day	-14 or -56	1	8	15	29	57	84	168, 252, 336...		(Last dose +40 days)	
Visit Window f	±3d	±2d	±2d	±2d	±2d	±2d	±2d	±7d		±7d	
Procedure/activity											
Date of first receipt of rescue therapy											X

AChR=acetylcholine receptor; AE=adverse event; ALP=alkaline phosphatase; ALT=alanine aminotransferase; AST=aspartate aminotransferase; C5=complement component 5; COVID-19=coronavirus disease 2019; C-SSRS=Columbia-Suicide Severity Rating Scale; ECG=electrocardiogram; EW=Early Withdrawal; FDA=Food and Drug Administration; gMG=generalized myasthenia gravis; IV=intravenous; MG=myasthenia gravis; MG-ADL=Myasthenia Gravis-Activities of Daily Living; MGFA=Myasthenia Gravis Foundation of America; MG-QOL15r=Myasthenia Gravis-Quality of Life Revised; PD=pharmacodynamic(s); PLEX=plasma exchange; PK=pharmacokinetic(s); QMG=Quantitative Myasthenia Gravis; SAE=serious adverse event; SC=subcutaneous(ly); SFU=Safety Follow-up; SOC=standard of care; sRBC=sheep red blood cell; TSQM-9=9-item Treatment Satisfaction Questionnaire for Medication; ZLP=zilucoplan

a The Screening Visit should be scheduled to coincide with the regularly scheduled study participant IV C5 inhibitor administration (±3 days) (Figure 1-1).

b If a study participant permanently withdraws from the study prior to the Week 12 visit, the study participant should return to the clinic for an EW Visit as soon as possible but no later than the next scheduled visit.

c Study participants who discontinue ZLP at any point in the study will be required to return to the clinic for a SFU Visit performed at 40±7 days after their last dose to gather additional safety information, including information about on ongoing AEs and the reporting any new SAEs since the last study visit.

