**Table 1-2: Schedule of Activities**

Study Period	Screening Period a	Main Treatment Period						Extension Treatment Period	EW/ Withdrawal Visit b,w	SFU Visit (In-clinic) c	Rescue Therapy Visit (If applicable) d
		Baseline e (In-clinic)	Week 1 (Phone call)	Week 2 (In-clinic)	Week 4 (Phone call)	Week 8 (Phone call)	Week 12 (In-clinic)				
Visit name	Screening Visit (In-clinic)							Week 24, 36, 48... every 12 weeks (In-clinic)			
Visit #	1	2	3	4	5	6	7	8, 9, 10...	–	–	–
Day	-14 or -56	1	8	15	29	57	84	168, 252, 336...		(Last dose +40 days)	
Visit Window f	±3d	±2d	±2d	±2d	±2d	±2d	±2d	±7d		±7d	
Procedure/activity											

f The visit windows provided are with respect to the Baseline Visit with the exception of the SFU Visit, in which the visit window applies to 40 days after the last dose of study medication.

g Procedures performed as SOC during the Screening Period may be used to determine eligibility. Informed consent must be obtained prior to performing any study-specific procedures that are not SOC.

h Screening includes disease history with documented diagnosis of gMG by the MGFA criteria (Class II-IVa) and documented serology for AChR autoantibodies.

i Height will be measured only at Screening.

j All prescriptions and over-the-counter medications taken during the 30 days prior to Screening through the last study visit will be documented. Note: A complete history of medications taken for the treatment of gMG will be collected.

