SC. Following in-clinic education and training, all study participants will self-inject daily SC doses of study medication for the subsequent 12 weeks. Single-use pre-filled syringes in injection devices will be provided for use during the study. Of note, there will be no washout period during the study where study participants are not receiving treatment for MG.

During the Main Treatment Period, study participants will be contacted via phone call at Week 1, Week 4, and Week 8 to assess safety and tolerability. During these phone call visits, the MG-ADL assessment will also be performed. Study participants will return to the clinic at Week 2 and Week 12 to evaluate safety, tolerability, and efficacy. Additional assessments will include questionnaires, PK, and PD. Safety assessments will include AE monitoring, physical examination, clinical laboratory tests, and Columbia-Suicide Severity Rating Scale (C-SSRS) in accordance with the Schedule of Activities (Section 1.3).

The time needed for preparation and administration of SC ZLP will also be measured during the Screening Period and Main Treatment Period in accordance with the Schedule of Activities (Section 1.3).

Study participants are expected to remain on a stable dose regimen of all medications unless medically indicated changes become necessary. All SOC therapy medications for gMG should be kept at the same dose regimen throughout the Main Treatment Period, including corticosteroids and immunosuppressant therapy (IST) drugs. If rescue therapy becomes necessary due to major deterioration of a study participant's clinical status, or risk of MG crisis as per the Investigator's judgment, the study participant may receive IVIG or PLEX treatment as rescue therapy (Section 6.5.4).

Additionally, if deemed needed as per the Investigator's judgment, study participant may be readministered their previous IV C5 inhibitor or administered a different IV C5 inhibitor after discontinuation of the study medication.

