If a study participant withdraws from the study, the participant should immediately stop the intake of the study medication and will be required to return to the clinic for an EW/Withdrawal Visit (depending on whether the participant withdrew during the Main Treatment Period or during the Extension Treatment Period) as soon as possible but no later than the next scheduled visit and for a SFU Visit  $40\pm7$  days after their last dose of study medication to gather information on ongoing AEs and report any new SAEs since the last study visit (Section 1.3).

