1.1 Objectives and Estimands/Endpoints

The estimand corresponding to the primary objective and primary safety analyses are described below. The estimands corresponding to the secondary objectives and secondary analyses are also described below.

Table 1.1: Objectives and estimands/endpoints

Objectives	Estimands/endpoints
Primary	
To evaluate the safety and tolerability of switching from intravenous (IV) Complement component 5 (C5) inhibitors to subcutaneous (SC) Zilucoplan (ZLP) in study participants with generalized Myasthenia Gravis (gMG)	
The primary safety endpoints are:
 
• Incidence of Treatment Emergent Adverse Events (TEAEs) over the Main Treatment Period• Incidence of TEAEs leading to withdrawal of study medication over the Main Treatment Period
Secondary	
To evaluate the efficacy of SC ZLP after switching from IV C5 inhibitors in study participants with gMG	The secondary efficacy estimand is:

Objectives	Estimands/endpoints
	
 Treatment: ZLP administered by daily SC injections (0.3mg/kg/day) Target population: Adult study participants with gMG currently receiving an IV C5 inhibitor approved for the treatment of gMG according to the protocol-specified inclusion/exclusion criteria Endpoint: Change from Baseline (CFB) to Week 12 in Myasthenia Gravis -Activities of Daily Living (MG-ADL) score Intercurrent event handling: The intercurrent events considered in this study are: 
 ICE1: Administration of rescue therapy or changes in Standard of Care (SoC) dose regimens. Data collected at and after the point of the intercurrent event will be used as collected to gain understanding of clinical practice. ICE2: Participant discontinuation from the study. It will be assumed that the participant had remained on their treatment (regardless of rescue therapy administration) throughout the study (i.e., a "hypothetical strategy" assuming participants did not discontinue the study and remained on treatment). Population level summary: The mean of the endpoint

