To evaluate the efficacy of SC ZLP after switching from IV C5 inhibitors on an additional efficacy endpoint in study participants with gMG	
The secondary efficacy endpoint is:
 
 CFB to Week 12 in the Quantitative Myasthenia Gravis (QMG) score 
This endpoint will be analyzed following the same estimand structure as defined for the MG-ADL score. The endpoint assessed will change accordingly.

To evaluate safety and tolerability of SC ZLP after switching from IV C5 inhibitors on additional safety measures in study participants with gMG	
The secondary safety endpoints are:
 
 Incidence of serious TEAEs over the Main Treatment Period Incidence of study withdrawal over the Main Treatment Period
Other	
To further explore the efficacy of SC ZLP on additional efficacy endpoints after switching from IV C5 inhibitors in study participants with gMG	
The other efficacy endpoints are:
 
 Time to first receipt of rescue therapy over the Main Treatment Period Change in SoC therapy medication dose regimen for gMG during the Main Treatment Period

Objectives	Estimands/endpoints
	
 • Achievement of Minimal Manifestation Status per Myasthenia Gravis Foundation of America Post Intervention Status (MGFA-PIS) at Week 12 without rescue therapy • Achieving minimal symptom expression (MSE), defined as an MG-ADL of 0 or 1 at Week 12 without rescue therapy • CFB to Week 12 in QMG subscores: ocular, bulbar, respiratory, limb • CFB to Week 12 in Myasthenia Gravis MG Quality of Life 15 Item scale revised (MG-QOL15r) score • MG-ADL score responder rate (responder is defined as achieving \geq 3-point improvement from Baseline [decrease] at Week 12 and not having taken rescue therapy) • QMG score responder rate (responder is defined as achieving \geq 5-point improvement from Baseline [decrease] at Week 12 and not having taken rescue therapy)
To explore the time needed for administration of SC ZLP	
The other endpoint is:
 
 • Time needed for administration of SC ZLP
To explore study participants' treatment satisfaction following the use of SC ZLP	
The other endpoint is:
 
 • CFB to Week 12 in 9 item Treatment Satisfaction Questionnaire for Medication (TSQM-9) scores

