5.1.1.1.4 Mapping of assessments performed at (Early) Withdrawal Visit

If a participant prematurely discontinues study drug at any time prior to Week 12 during the Main Treatment Period, the participant should return to clinic for a stand-alone EW Visit. If a participant withdrew during the Extension Treatment Period, the participant should perform a Withdrawal Visit. These assessments will be mapped to the next scheduled visit where each assessment is evaluated as per protocol. This approach means that there is a chance that EW (or Withdrawal) data will be mapped to different visits according to the schedule of assessments.

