5.3.1.1.3 Handling of missing data

The number of missing values by visit for the main secondary efficacy endpoint will be provided using descriptive statistics on the mITT. Additionally, the number of missing values by visit due to COVID-19 will be summarized for the main secondary efficacy endpoint (using the “COVID-19 Impact” e-CRF page) as explained in Section 5.2.

For secondary efficacy analyses, missing data will be handled according to the secondary efficacy estimand definition:

- For missing data of participants that discontinue from the study, a missing at random assumption will be used for imputation.
- For other missing data, the same missing at random assumption as the one used for imputing missing data of participants that discontinue from the study will be applied.

The MMRM that will be used to model the CFB to Week 12 in MG-ADL score consider missing data with the missing at random assumption.

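### Early Withdrawal scores are analysed as Week 12 with no day limit, which bypasses the on-treatment (MAR) handling of withdrawals, and no planned analysis clearly shows Week 12 without them

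*SAP*

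**What the plan says.** **Mapping.** SAP 5.1.1.1.4 states of EW assessments: "These assessments will be mapped to the next scheduled visit where each assessment is evaluated as per protocol". It notes that different assessments from one EW Visit may land on different visits. SAP 5.1.1.1 makes this the only visit mapping in the analysis.

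**Timing and drug status.** Under protocol Table 1-2, footnote b, "the study participant should return to the clinic for an EW Visit as soon as possible but no later than the next scheduled visit". On withdrawal, "the participant should immediately stop the intake of the study medication" (protocol 7.2). MG-ADL is scheduled at Weeks 1, 2, 4, 8 and 12. QMG is done after Baseline only at the two clinic visits: "Study participants will return to the clinic at Week 2 and Week 12 to evaluate safety, tolerability, and efficacy" (protocol 4.1). Main Treatment Period windows are ± 2 days, and "The visit windows provided are with respect to the Baseline Visit with the exception of the SFU Visit".

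**Estimand.** Study discontinuation (ICE2) has a hypothetical strategy, "assuming participants did not discontinue the study and remained on treatment" (SAP 1.1). For QMG, "This endpoint will be analyzed following the same estimand structure as defined for the MG-ADL score". SAP 5.3.1.1.3 implements this through the MMRM, which is said to "consider missing data with the missing at random assumption".

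**Sensitivity analyses.** For MG-ADL the SAP plans a t-test on observed Week 12 data, a t-test using the worst score for participants with an intercurrent event, and a Wilcoxon test with worst observation carried forward. The QMG section (5.3.1.2.2) refers to 5.3.1.1.2 and 5.3.1.1.3, not to the sensitivity section 5.3.1.1.4, and rules out testing.

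**The concern.** The mapping is stated openly. The difficulty is that it and the estimand pull in different directions. The estimand wants a 12-week on-treatment value for a participant who left and relies on MAR to supply it. The mapping puts an earlier, post-stopping score into the Week 12 cell. That cell is then not missing, so the MMRM treats the score as an ordinary Week 12 observation and the ICE2 handling does not operate for it. EW MG-ADL scores mapped to Weeks 1 to 8 enter the model in the same way.

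At stake is the Week 12 MG-ADL comparison with the 2-point margin, which is the study's only formal efficacy test, and the descriptive QMG result. With 20 participants and no replacement, a few mapped values can matter, and no planned estimate isolates their contribution.

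**Working it through.** **1. Days that map to Week 12.** Table 1-2 gives MG-ADL on Days 1, 8, 15, 29, 57 and 84, and QMG on Days 1, 15 and 84. The next scheduled visit is Day 84 for MG-ADL on Days 58-83 and for QMG on Days 16-83. The Week 12 window is 84 ± 2 = Days 82-86, so Days 82-83 are legitimately Week 12.
- Outside the window: MG-ADL Days 58-81 (81 − 58 + 1 = 24 days); QMG Days 16-81 (81 − 16 + 1 = 66 days).
- The lower ends are approximate. The Week 8 window is Days 55-59 and the Week 2 window Days 13-17, so Days 58-59 or 16-17 may belong to a visit still pending.

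**2. How early, and how long off drug.** Days early = 84 − d. Maximum days off drug = d minus the previous scheduled visit day, because the EW Visit is due by the next one. Residual exposure assumes simple decay with half-life 40/5 = 8 days (protocol 5.1): 0.5^(t/8).

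| Scale, EW day | Days early | Max days off drug | Residual at that maximum |
|---|---|---|---|
| MG-ADL, 58 | 26 | 1 | 92% |
| MG-ADL, 70 | 14 | 13 | 32% |
| MG-ADL, 81 | 3 | 24 | 12% |
| QMG, 16 | 68 | 1 | 92% |
| QMG, 57 | 27 | 28 | 9% |

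The earliest values are the least off drug, and the reverse.

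**3. The planned analyses.**
- The observed-data t-test does not say whether mapped values count as observed.
- The worst-score and worst-observation rules are harsher than either alternative and can select the EW score itself.
- QMG cites no part of the sensitivity section.

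**4. The plan's own figure.** SE = 3/√20 = 0.671; noncentrality = 2/0.671 = 2.981; the noncentral t with 19 df gives power 80.7%, matching the stated 80%. At an observed SD of 3, noninferiority needs a mean below 2 − 2.093 × 0.671 = 0.596. If k mapped values each differ by d points from the unseen on-treatment value, the mean moves by k·d/20, which is 0.05 per value per point.

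**5. Illustration A: a fixed difference d** (SD 3, true change 0; k and d are assumptions; t-test standing in for the MMRM).

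| Rule | k = 1 | k = 2 | k = 4 |
|---|---|---|---|
| Mapped, d = +3: shift in mean | +0.15 | +0.30 | +0.60 |
| Mapped, d = +3: pass probability | 73% | 64% | 45% |
| Mapped, d = +1 | 79% | 76% | 71% |
| Mapped, d = 0 | 81% | 81% | 81% |
| Mapped, d = −2 | 84% | 87% | 91% |
| Left missing (n = 19, 18, 16) | 78% | 76% | 70% |

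Here k counts mapped values, not withdrawers. If EW Visits fell uniformly over Days 2-83 (assumption), 24/82 would be out-of-window Week 12 MG-ADL values, so k = 1, 2 or 4 implies k × 82/24 = 3.4, 6.8 or 13.7 withdrawers.

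**6. Illustration B: informative withdrawal, no off-drug effect.** Scores at Week 8, EW and Week 12 each have SD 3 and true mean 0, adjacent correlation r and Week 8-Week 12 correlation r². The exclusion rule regresses Week 12 on Week 8 in completers and evaluates at the all-participant Week 8 mean. Bias in the Week 12 mean for k = 2 (simulation error about 0.01):

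| Who withdraws | Rule | r = 0.5 | r = 0.7 | r = 0.85 |
|---|---|---|---|---|
| Worst EW scores | Mapped | +0.24 | +0.14 | +0.08 |
| Worst EW scores | Excluded | −0.22 | −0.23 | −0.15 |
| Would be worst at Week 12 | Mapped | −0.24 | −0.15 | −0.07 |
| Would be worst at Week 12 | Excluded | −0.52 | −0.45 | −0.30 |

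Negative bias favours noninferiority. In the last two rows both rules err the same way.

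**The case against.** The strongest reply is that the mapping may be the better rule. An EW score is the last one seen in the study and may show the deterioration that led to withdrawal. Dropping it makes MAR less plausible. Illustration B supports this: exclusion is more biased than mapping in most cells, and always toward noninferiority. That stands, and it is why the mapped analysis should stay.

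Other parts also stand in some measure:
- Protocol 4.2 reports that the separation from placebo in the pivotal study was greatest within 4 weeks and then held to Week 12. Being early is therefore not in itself evidence of bias for an MG-ADL from Day 58 on.
- The days off drug are maxima. The EW Visit is due as soon as possible and may follow the last dose closely.
- The SAP plans listings of MG-ADL changes and of all intercurrent events, plus individual line plots for MG-ADL and QMG. With 20 participants, a reader could trace withdrawers by hand. That still gives no estimate without the mapped values.
- The worst-score t-test does probe dependence on withdrawers for MG-ADL, but by a harsher rule.

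A reader might infer that the mapping is known to bias the noninferiority test, or that the fall to 45% is to be expected. The documents give no withdrawal rate and no post-stopping change, so neither is supported. That fall needs four mapped values, each 3 points worse.

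**Conclusion.** The conflict holds on the text. For out-of-window EW scores, the mapping fills a cell that the estimand would treat under MAR, and no planned analysis clearly shows the Week 12 result without those scores, for either scale. The nominal ranges are about Day 58-81 for MG-ADL and Day 16-81 for QMG.

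Size and direction are unknown, and the effect is zero if nobody withdraws in those ranges. Every effect figure above rests on assumed numbers of mapped values, differences and correlations, with simple models in place of the MMRM. Either rule can favour or disfavour noninferiority.

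Two further inferences are tempting and not supported. One is that exclusion should replace the mapped main analysis; under informative withdrawal it can be the more biased rule. The other is that the true mean must lie between the two results; in the last scenario it lies outside both. Showing both results tells the reader how far the conclusion depends on the rule. It does not bound the truth.

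The primary endpoints are safety and QMG is not tested, so the consequence for inference is confined to the MG-ADL noninferiority test.

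**What to change.** 1. Flag every EW-derived MG-ADL and QMG record, with its actual study day.
2. Add a named MMRM analysis for both scales that uses an EW value at a scheduled visit only if its actual day lies in that visit's protocol window (Day 84 ± 2 for Week 12). Otherwise leave the cell missing under MAR.
3. Report it beside the mapped analysis. Say which of the two is taken to target ICE2, and whether the MG-ADL noninferiority conclusion is the same in both. QMG stays descriptive.
4. State in SAP 5.3.1.1.4 that the observed-data t-test at Week 12 excludes out-of-window mapped EW values.

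The mapped main analysis can remain. The cost is SAP wording, one derivation flag and one extra model run per scale, with no change to data collection. The added analysis has a slightly wider interval: under the assumptions of illustration B with random withdrawal, the SE of the Week 12 MG-ADL mean is about 0.68 to 0.76 with 1 to 4 values missing, against 0.67 with all 20.

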5.1.1.1.5 Definition of Baseline values

Unless otherwise specified, Baseline will be the last available pre-dose value prior to the first injection of IMP in the Main Treatment Period, or if missing, the Screening value. Scheduled or unscheduled measurements can be used as the Baseline value. If a Baseline measurement is not available but an unscheduled measurement occurs after the planned baseline measurement time point but before dosing, then the unscheduled measurement will be used.

Change from Baseline (CFB) is defined as the value minus baseline value. Percent Change from Baseline is defined as $100 \times (\text{Change from Baseline} / \text{Baseline})$.

5.1.1.2 Protocol Deviations

Analyses related to protocol deviations are given in Appendix 6.1.2.

5.1.1.3 Treatment assignment and treatment groups

Treatment group will be shown as: Zilucoplan 0.3mg/kg.

5.1.1.4 Center pooling strategy

It is planned to recruit study participants in different sites in North America in this study. The data from all sites will be pooled for analyses.

5.1.1.5 Coding dictionaries

Adverse events (AEs) and medical histories will be coded using version 24.0 or later of the Medical Dictionary for Regulatory Activities (MedDRA®).

Medications will be coded according to version March 2021 or later of the World Health Organization Drug Dictionary (WHODD).

5.1.1.6 Multicenter studies

Individual center results will not be displayed.

5.1.1.7 Missing data

5.1.1.7.1 Efficacy endpoints

For secondary efficacy analyses, missing data will be handled according to the secondary efficacy estimand definition:

- For missing data of participants that discontinue from the study, a missing at random assumption will be used for imputation. This is in relation to the assumption that the participant had remained on their treatment throughout the study.
- For other missing data, the same missing at random assumption as the one used for imputing missing data of participants that discontinue from the study will be applied.

5.1.1.7.2 Safety, PK and PD endpoints

Missing data for Safety, PK and PD endpoints will not be imputed; observed cases will be used. This will include observations occurring after a participant receives rescue-medication.

